of men undergoing radical treatment will demonstrate treatment failure. It is hypothesised that radical treatment may be superior to PA in terms of oncological efficacy, but that radical treatment is considerably inferior to PA in terms of functional outcomes. The anticipated worse HRQoL with radical treatment compared with PA, in particular functional outcomes such as urinary continence, erectile function, and bowel toxicity, leads us to consider that radical treatment would need to achieve a 10% lower primary treatment failure rate (e.g. 10% compared to 20%) for it to remain the preferable option in clinical practice. This study is therefore a superiority trial, with treatment failure, and HRQoL and functional outcomes, hypothesised to be superior for PA versus radical treatment. Allowing for a 10% total dropout rate across the entire study, 800 patients randomised on a 1:1 basis to radical treatment or PA would provide approximately 88% power at p < 0.025 to detect a $\geq 10\%$ lower treatment failure rate (10% versus 20%, a hazard ratio of $0.4722 = \log(0.9)/\log(0.8)$) with radical treatment compared to PA treatment. The statistical power would not be much affected if the failure rate in the radical treatment group was somewhat lower, or somewhat higher, than 15%. For example, 800 patients (with 10% dropout) would provide approximately 79% power at p<0.025 to detect a difference of 15% versus 25% in failure rates (hazard ratio 0.5649 = log(0.85)/log(0.75)) and over 95% power to detect a 5% versus 15% failure rate (hazard ratio 0.3156 = log(0.95)/log(0.85)). With 800 patients randomised (and 10% lost to follow-up in total across the study), numerous sample size calculations using various parameters indicate that there will be ample statistical power to detect any meaningful differences in HRQoL scores, e.g. over 90% power at p<0.01 to detect a small to moderate (0.3sd) effect size. Put in perspective, this is a considerably smaller effect size than the 0.5sd effect size described by Norman et al (37) as the minimally important difference for HRQoL differences.

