The primary analysis is planned in the final six-months of the seven-year study, at which point median follow-up (from randomisation) will be approximately 3 years. To allow for having two co-primary outcome measures, adjustment for multiplicity has been made using Bonferroni's adjustment and therefore a *p*-value of <0.025 will be considered statistically significant for each co-primary endpoint. 95% confidence intervals of comparative treatment effects will be reported.

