19.9 Level of Statistical Significance

To allow for having two co-primary outcome measures, a *p*-value of <0.025 will be considered statistically significant. A *p*-value of less than 0.05 will be considered statistically significant for all secondary and tertiary endpoints. 95% confidence intervals will be reported for treatment effects.

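### Bonferroni for the two co-primaries is valid, but Holm's step-down has the same 5% familywise error, never rejects less, and could add up to about 5 to 7 points of treatment-failure power

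*Protocol*

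**What the plan says.** Section 19.4 names the method, "adjustment for multiplicity has been made using Bonferroni's adjustment", and sets the rule: a p-value of "<0.025 will be considered statistically significant for each co-primary endpoint". Section 19.9 gives the same threshold and the same reason: "To allow for having two co-primary outcome measures". Neither section lets the result on one endpoint change the threshold for the other, and neither says why Bonferroni was preferred.

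Section 19.2 sizes the trial to that threshold, with "800 patients randomised on a 1:1 basis to radical treatment or PA" and a 10% total dropout. For treatment failure ("10% versus 20%, a hazard ratio of" 0.4722) the design "would provide approximately 88% power at p < 0.025". For 15% versus 25% (hazard ratio 0.5649) it "would provide approximately 79% power at p<0.025". For HRQoL, section 19.2 states over 90% power at p<0.01 for a 0.3 SD effect.

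On intervals, section 19.4 says that "95% confidence intervals of comparative treatment effects will be reported", so 95% intervals will stand beside tests made at 0.025.

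**The concern.** As section 19.4 is written, either co-primary can be declared significant on its own, which is the setting where a familywise correction is needed. In that setting Bonferroni is the simplest valid rule, but Holm dominates it: the error bound is the same and its rejections always include Bonferroni's.

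The difference could matter here because treatment failure is the less well powered of the two endpoints, with a stated 79% in one of the protocol's own scenarios. Section 19.3 chose the pair to show a trade-off between cancer control and function, so a clear answer on both endpoints is worth having. If PORPUS-P reaches 0.025, Holm tests treatment failure at 0.05 instead of 0.025.

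**Working it through.** **Inputs (section 19.2).** 800 patients at 1:1 less 10% dropout: 360 per arm. Stated treatment-failure power 88% and 79% at 0.025. HRQoL effect 0.3 SD. The protocol does not state sidedness; two-sided tests are assumed. Critical values: 2.2414 at 0.025, 1.96 at 0.05, 2.576 at 0.01.

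**The plan's own figures**
- HRQoL: expected z = 0.3 × √(360/2) = 4.02. Power at 0.01 = Φ(4.02 − 2.576) = 92.6%, which agrees with the stated figure of over 90%. At 0.025 it is Φ(4.02 − 2.2414) = 96.3%.
- Treatment failure, 10% v 20%: events = 360 × 0.10 + 360 × 0.20 = 108. Schoenfeld: |ln 0.4722| × √(108/4) = 3.90, power Φ(3.90 − 2.24) = 95.1%. Freedman: (0.5278/1.4722) × √108 = 3.73, power 93.1%. Comparing two proportions gives 93.7%, or 92.3% with continuity correction. The stated 88% is not reproduced directly. It is approached (87.6%, with 77.4% against the stated 79%) if the rates are read as 5-year rates, with 5 years of uniform accrual, at least 1 year of follow-up and 10% exponential dropout over 5 years.

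Because of this, the gain is worked out from both the stated and the recomputed powers.

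**Error rate.** If both nulls are true, Holm errs only when the smaller p-value is below 0.025, exactly when Bonferroni errs, so the probability is at most 5%. If one null is true, an error requires that p-value to be below 0.05. Two million simulated pairs with correlations from −0.9 to 0.9 agree: at most 4.97% with both nulls true (the same as Bonferroni) and at most 4.9% with one true.

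**Power.** For independent test statistics:

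Holm power = P(0.025) + [P(0.05) − P(0.025)] × Q(0.025),

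where P is treatment-failure power and Q is PORPUS-P power.

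- Stated 88%: implied z = 1.175 + 2.2414 = 3.416, so P(0.05) = Φ(3.416 − 1.96) = 92.7%. Holm = 0.880 + 0.047 × 0.963 = 92.6%.
- Stated 79%: implied z = 3.048, P(0.05) = 86.2%. Holm = 0.790 + 0.072 × 0.963 = 85.9%.
- PORPUS-P itself, at 0.3 SD beside 88%: 96.3% becomes 97.8%.
- Both endpoints significant: Bonferroni 0.88 × 0.963 = 85%. Holm, 0.927 × 0.981 less the small probability that both p-values lie between 0.025 and 0.05, gives 91%.

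**Sensitivity** (simulation; the 0.2 SD row values are assumptions, not protocol figures)

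| Bonferroni power, treatment failure | True PORPUS-P effect | Holm, independent | Holm, correlation −0.5 to 0.5 |
|---|---|---|---|
| 88% (stated, 10% v 20%) | 0.3 SD | 92.6% | 92.3-92.7% |
| 88% | 0.2 SD | 91.2% | 89.9-92.3% |
| 88% | none | 88.1% | 88.1-88.2% |
| 79% (stated, 15% v 25%) | 0.3 SD | 85.9% | 85.7-86.1% |
| 79% | 0.2 SD | 83.8% | 82.5-85.1% |
| 79% | none | 79.2% | 79.1-79.2% |
| 93.1% (Freedman, 10% v 20%) | 0.3 SD | 96.0% | 95.7-96.1% |
| 95.1% (Schoenfeld, 10% v 20%) | 0.3 SD | 97.3% | 97.0-97.4% |
| 86.3% (Freedman, 15% v 25%) | 0.3 SD | 91.3% | 91.1-91.5% |

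**The case against.** - **Nothing is wrong as written.** The threshold is the same in sections 19.2, 19.4 and 19.9, and the trial was sized to it. This stands: the point is an improvement, not a correction.
- **The gain hangs on PORPUS-P.** Section 19.2 gives 0.3 SD as an effect the trial could detect, not as a forecast. Section 7.7 reports no significant difference in overall HRQoL in the feasibility study, though only 71 men were analysed. This stands, and is why the gain is given as a range starting at zero.
- **The baseline powers are uncertain.** This also stands. From the recomputed 93-95% the gain is about 2 to 3 points.
- **Separate thresholds are easier to explain.** The endpoints are expected to favour opposite arms, so under Holm a treatment-failure result of p=0.03 in favour of radical treatment would count only because PORPUS-P was also significant, perhaps in favour of partial ablation. That is awkward to explain but properly error-controlled, and does not outweigh a rule that never loses power.
- **Holm needs a single PORPUS-P p-value.** Section 19.4 describes a repeated-measures model with a treatment-by-visit interaction, and the contrast may be settled in the SAP. Bonferroni needs one p-value too, so this is a condition of the change and not an argument against it.
- **Intervals.** A reader might infer that, because 95% intervals already sit beside 0.025 tests, Holm's known weakness over matching intervals is irrelevant here. That goes too far. Under Bonferroni, 97.5% intervals would restore the match. Under Holm they can disagree with the test: p=0.03 corresponds to z=2.17, below 2.24, so the 97.5% interval includes the null although the step-down test at 0.05 is significant.

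**Conclusion.** Sections 19.4 and 19.9 fix a valid rule when a uniformly more powerful one with the same familywise error is available. The gain in treatment-failure power is about 0 to 5 points from the stated 88% and about 0 to 7 points from the stated 79%. The upper ends assume a true PORPUS-P effect near 0.3 SD, two-sided tests and the protocol's own starting powers.

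A reader might infer that the plan throws away 5 to 7 points of oncological power for nothing. The documents do not support that. The figure is conditional on an HRQoL effect that the protocol does not predict, the starting powers do not follow directly from the stated inputs, and Holm carries a small cost in interval reporting. This is a desirable change of low severity.

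**What to change.** In sections 19.4 and 19.9, replace Bonferroni by Holm: test the smaller of the two co-primary p-values at 0.025; if it is significant, test the other at 0.05; otherwise declare neither significant. State that the PORPUS-P p-value comes from one pre-specified contrast of the repeated-measures model, and make sure the SAP names it.

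Keep the planned 95% intervals. If 97.5% intervals are added, say that they may include the null when the step-down test is significant.

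Make the change, dated and documented, before any comparative data are seen. Section 19.7 plans no formal interim analysis of treatment effects, but section 15.5 leaves the statisticians unblinded so that they can prepare closed reports for the monitoring committee, so earlier is better. The cost is a short amendment to two sections, no extra patients, and slightly less simple interval reporting. The sample size need not change.

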19.4 Description of Statistical Methods

The primary analysis will be performed according to the Intention-To-Treat principle. Treatment failure will be compared between radical treatment and PA treatment using survival analysis techniques. Statistical significance between treatment groups will be assessed using log rank methods, and Kaplan-Meier survival curves will be used for graphical representation. Patients without treatment failure will be censored at time of death or time of last follow-up. Additional supporting analyses will be undertaken using Cox proportional hazards regression models adjusting for stratification factors and time from randomisation to start of treatment. Patients without treatment failure will be censored at their last known treatment failure free time.

For PORPUS and the other disease-specific HRQoL outcomes, Mixed Models for Repeated Measures (MMRM) will be used to evaluate differences over time by treatment group. MMRM models will be adjusted for treatment, baseline score, stratification factors, visit and a treatment by visit interaction as fixed effect terms, with patient included as a random effect. Differences between treatment groups will be reported as mean difference with 95% confidence intervals. Absolute and percentage average changes in HRQoL outcomes from baseline assessment will be displayed graphically. HRQoL forms that are returned partially complete will be analysed according to the scoring instructions for each questionnaire. The MMRM analyses will minimise the impact of missing data so the use of multiple imputation or other methods for dealing with missing data is not planned. Survival analysis techniques, as described for the treatment failure primary outcome, will also be used to compare differences between radical treatment and PA treatment for time to disease progression (including metastases), time to disease-specific mortality, and time to all-cause mortality. Patients without

disease progression at time of analysis will be censored at time of death or time of last known alive date.

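### Each co-primary endpoint is tested at p<0.025, but its treatment effect is to be reported with a 95% interval, which corresponds to p<0.05

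*Protocol*

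**What the plan says.** Section 19.4 says that "adjustment for multiplicity has been made using Bonferroni's adjustment", so that a p-"value of <0.025 will be considered statistically significant for each co-primary endpoint". The next sentence sets the interval level: "95% confidence intervals of comparative treatment effects will be reported". Earlier in the same section, for PORPUS and the other disease-specific quality-of-life scores, it says: "Differences between treatment groups will be reported as mean difference with 95% confidence intervals".

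Section 19.9 repeats the pairing. It gives the 0.025 threshold for the co-primaries and adds that a p-"value of less than 0.05 will be considered statistically significant for all secondary and tertiary endpoints". It then closes with one interval level for everything: "95% confidence intervals will be reported for treatment effects".

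No section gives a 97.5% or otherwise adjusted interval for the co-primaries. No section says whether the tests are one-sided or two-sided.

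**The concern.** The p-value threshold changes between co-primary endpoints (0.025) and the other endpoints (0.05), but the interval level does not. With two-sided tests, 95% is therefore the matching level only for the secondary and tertiary endpoints. A co-primary result with p between 0.025 and 0.05 would be published as not significant beside an interval that excludes no effect.

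This matters because section 19.3 chose the two co-primaries to show a trade-off between cancer control and function. Readers will weigh two estimates and their intervals together. If one interval appears to show a difference that the test does not support, the trade-off is open to competing readings. An interval level chosen after the data are seen would look selective.

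**Working it through.** **Inputs.** Alpha of 0.025 per co-primary and 0.05 for other endpoints (19.4, 19.9). Interval level of 95% throughout (19.4, 19.9). From 19.2: 800 men, 1:1, 10% dropout (360 per arm); 88% power at p<0.025 for 10% v 20% failure (hazard ratio 0.4722); 79% power for 15% v 25%. Assumption: two-sided tests.

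**1. The plan's own figure.** Bonferroni over two endpoints: 0.05/2 = 0.025. This reproduces the stated threshold.

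**2. Matching interval.** A two-sided test at level α corresponds to a 100(1−α)% interval.
- α = 0.025: 97.5% interval, critical value 2.2414.
- α = 0.05: 95% interval, critical value 1.9600.
- Ratio of widths: 2.2414/1.9600 = 1.144, so 97.5% intervals are 14.4% wider.

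**3. Joint coverage of the two co-primary intervals** (Bonferroni bound, no independence needed).
- Two 95% intervals: at least 1 − 2×0.05 = 90% (0.95² = 90.25% if independent).
- Two 97.5% intervals: at least 1 − 2×0.025 = 95% (0.975² = 95.06% if independent).

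**4. Probability of a conflict for treatment failure.** If the test statistic is normal with mean μ and unit variance, the conflict probability is Φ(2.241 − μ) − Φ(1.960 − μ). The stated power gives μ = 2.241 + z(power).
- 88% power: μ = 2.241 + 1.175 = 3.416. Conflict = Φ(−1.175) − Φ(−1.456) = 0.120 − 0.073 = about 4.7%.
- 79% power: μ = 2.241 + 0.806 = 3.048. Conflict = Φ(−0.806) − Φ(−1.088) = 0.210 − 0.138 = about 7%.
- No true effect: 0.05 − 0.025 = 2.5% per endpoint.

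If 108 events are assumed instead (360×10% + 360×20%), μ = |ln 0.4722|×√108/2 = 3.90 and the conflict probability is about 2.2%. That event count implies about 95% power rather than the stated 88%, so the figures above use the protocol's own power.

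**5. What a conflict looks like** (illustration with the assumed 108 events, standard error of the log hazard ratio 2/√108 = 0.192). An observed hazard ratio of 0.66 gives p = 0.031.

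| Interval | Limits | Includes 1? |
|---|---|---|
| 95% | 0.453 to 0.962 | no |
| 97.5% | 0.429 to 1.016 | yes |

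The zone of disagreement runs from about 0.650 to 0.686. For PORPUS-P, in a simple two-mean approximation with 360 per arm, the standard error is √(2/360) = 0.0745 SD. The zone is then 1.960×0.0745 = 0.146 SD to 2.241×0.0745 = 0.167 SD.

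**6. Sidedness.** A one-sided 0.025 test corresponds to a two-sided 95% interval, which would remove the mismatch for the co-primaries. But 0.05 for the other endpoints, read as one-sided too, corresponds to a two-sided 90% interval. Under either reading applied throughout, a single 95% level cannot match both thresholds.

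**The case against.** The strongest reply is that nothing inferential is wrong. Significance is decided by the p-value alone, and the 0.025 rule holds family-wise error at 0.05. No interval serves as a decision rule, and this is a superiority design with no margin to exclude. Conventional 95% intervals beside an adjusted test are a defensible choice for estimation, and a SAP could add adjusted intervals or label the 95% ones as unadjusted.

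Most of this stands, and it limits the point to reporting. It does not remove it. The protocol does not leave the level open: it fixes 95% three times, twice close beside the 0.025 threshold, and does not say that the co-primary intervals are unadjusted.

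Two further objections also stand. First, the protocol ties the Bonferroni adjustment only to what counts as significant. It nowhere states joint interval coverage as an aim, so a reader should not infer that the plan breaks such a promise. Second, treatment failure is tested by log-rank, while the Cox models are supporting and covariate-adjusted. A hazard-ratio interval from those models is not the exact inverse of the log-rank test, so the two can differ at any level. Moving to 97.5% brings them into line in general but cannot guarantee agreement.

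**Conclusion.** The inconsistency is real and confined to the reported intervals of the two co-primary endpoints. With two-sided tests, p between 0.025 and 0.05 yields a 95% interval that excludes no effect beside a result declared not significant: exactly for the PORPUS-P mean difference, approximately for the failure hazard ratio. For treatment failure the chance of this is about 4.7% at the stated 88% power and about 7% at the stated 79% power. Joint coverage of the pair is guaranteed only to be at least 90%; the 90.25% figure needs independence, which cannot be assumed for two outcomes in the same men.

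A reader might infer that the trial's type I error is inflated to as much as 10%. The documents do not support that. Such a rate would arise only if effects were claimed from whether either 95% interval excludes the null, and the protocol does not do this. Sample size, power and the formal tests are unchanged.

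The conclusion rests on two-sided testing, which the derivation of 0.025 as 0.05/2 and the 0.05 level for other endpoints suggest but the protocol does not state. The conflict probabilities also rest on a normal approximation.

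**What to change.** In sections 19.4 (the quality-of-life paragraph and the multiplicity paragraph) and 19.9, specify two-sided 97.5% confidence intervals for the two co-primary effects: the failure hazard ratio and the PORPUS-P mean difference. Keep 95% for secondary and tertiary endpoints. A 95% interval may be shown as well for a co-primary if it is labelled as unadjusted for multiplicity. State in the same place that the tests are two-sided.

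The cost is a change of wording and co-primary intervals about 14% wider. No extra participants, data or analyses are needed.

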19.5 Inclusion in analysis

All analyses will be on an intention-to-treat basis. This means that patients will be analysed as they are randomised irrespective of the treatment actually received. The intention-to-treat population will include all patients who have given their informed consent and for whom there is confirmation of successful allocation of a randomisation number.

19.6 Subgroup analysis

There are currently no proposed subgroup analyses planned.

19.7 Interim analyses and stopping rules

The main outcomes will be analysed as stated in the analysis plan once the study follow-up has been completed. No formal interim analyses of treatment effects are planned for any of the study outcomes.

As there are no formal comparative interim analyses included in the study, no stopping rules have been incorporated into the study design. An independent DSMC will review the accumulating data at regular intervals and may recommend pausing or stopping the study in the event of safety concerns, as specified in the DSMC Charter. The TSC will make any final decision to terminate the study if appropriate.

19.8 Internal pilot/Decision Points

An internal pilot phase to assess the feasibility of recruitment will be conducted. Stop-go criteria will be reviewed after 18 months of recruitment.

Stop-go criteria for the pilot phase are given in table 5 together with the definitions of how each will be measured.

Table 5: Stop-go criteria for internal pilot phase

Progression guidance	Number of participants recruited in 18 months
Continue with study – no action required	150+
Continue with study – action required:	100-149
 Review recruitment strategies and modify/monitor closely Report to TSC 	
Require review with potential to close study to recruitment	<100

The Trial Management Group (TMG) will closely monitor the progression criteria during the internal pilot, and together with the TSC and DSMC will perform a full review towards the end of the internal pilot. The TSC and funder would make the final decision to terminate the study.

The internal pilot phase will mirror the procedures and logistics undertaken in the main definitive study. It is intended that the study will progress seamlessly into the main phase, with internal pilot participants included in the final analysis.

19.9 Level of Statistical Significance

To allow for having two co-primary outcome measures, a *p*-value of <0.025 will be considered statistically significant. A *p*-value of less than 0.05 will be considered statistically significant for all secondary and tertiary endpoints. 95% confidence intervals will be reported for treatment effects.

19.10 Procedure for accounting for missing, unused and spurious data

The procedure for handling spurious or missing data will be described in the Statistical Analysis Plan, and the Data Monitoring and Sharing Plan. The study will attempt to collect data as completely as possible. It is recognised that in practice some patients may decline a study-related repeat prostate biopsy, particularly if their PSA and/or MRI imaging is stable. In that scenario, it will be recorded on the CRF that the patient declined a study repeat biopsy, and the patient will remain in the study and continue other aspects of clinical follow-up.

Missing data will be minimised by careful data management, information provided to participants and training of study staff. Missing data will be described with reasons given where available; the number and percentage of individuals in the missing category will be presented by intervention arm. All data collected on the database will be used, since only essential data items will be collected. No data will be considered spurious in the analysis since all data will be checked and cleaned before analysis.

